5.2. Exclusion Criteria

- 5.2.1. ECOG PS >2.
- 5.2.2. Patients with active extramedullary disease.
- 5.2.3. Active CNS involvement.
- 5.2.4. Pleural effusions or ascites.
- 5.2.5. \geq Grade 3 peripheral neuropathy within 14 days before enrollment.
- 5.2.6. Active uncontrolled infection or severe systemic infection (enrollment is possible after control of infection).
- 5.2.7. Myocardial infarction within ONE months prior to enrollment or has New York Heart Association (NYHA – appendix IV) Class III or IV heart failure, uncontrolled angina, severe uncontrolled ventricular arrhythmias, or electrocardiographic evidence of acute ischemia or active conduction system abnormalities. Prior to study entry, any ECG abnormality at screening has to be documented by the investigator as not medically relevant.
- 5.2.8. Pregnant or breastfeeding – methotrexate is Pregnancy Category X - has been reported to cause fetal death and/or congenital abnormalities. Confirmation that the subject is not pregnant must be established by a negative serum β -human chorionic gonadotropin (β -hCG) pregnancy test result obtained during screening. Pregnancy testing is not required for post-menopausal or surgically sterilized women.
- 5.2.9. Uncontrolled diabetes mellitus defined as a Hemoglobin A₁C $\geq 10\%$ in patients with a prior history of diabetes, prior to study enrollment.

- 5.2.10. Serious concomitant systemic disorders (e.g., active uncontrolled infection or uncontrolled diabetes) or psychiatric disorders that, in the opinion of the investigator, would compromise the safety of the patient or compromise the patient's ability to complete the study.
- 5.2.11. Other severe acute or chronic medical or psychiatric conditions, or laboratory abnormality that may increase the risk associated with study participation or investigational product administration or may interfere with the interpretation of study results and, in the judgment of the investigator, would make the patient inappropriate for enrollment in this study.
- 5.2.12. Any history of epilepsy or a seizure disorder or any known prior seizures.
- 5.2.13. Abnormalities on 12-lead electrocardiogram (ECG) considered by the investigator to be clinically significant.
- 5.2.14. Known immediate or delayed hypersensitivity reaction or idiosyncrasy to drugs chemically related to IGF or methotrexate.

6. Registration/Enrollment

Registration/enrollment will occur after the patient has signed the informed consent document and eligibility is confirmed, but before any treatment has been administered. To be eligible for registration/enrollment into this study, the patient must meet each criterion listed on the eligibility checklist and supported by the clinical documentation in the patient's medical record. A copy of the eligibility checklist is maintained by the Clinical Trials Office (CTO) and can be found for each individual subject within the subject shadow chart. Patients must be registered/enrolled on the study within 30 days of signing the informed consent document. If the patient cannot be registered/enrolled within this timeframe, the patient may later be reconsidered for participation as outlined in section 6.3 below.

6.1. Registration/Enrollment with the Clinical Trials Office

Upon obtaining informed consent, completion of the screening evaluation, and verifying eligibility, the site study coordinator or designee will enroll the patient into EDC Easy®, the CTO Clinical Trials Management System (CTMS). The eligibility checklist must be completed by the study coordinator and verified/confirmed by the Principal Investigator or her designee (i.e., a sub-Investigator).

6.2. Registered/Enrolled Patients Who Do Not Begin Study Treatment

If a patient signs the informed consent document, is subsequently registered/enrolled to the study but is then not able to begin the planned study treatment for any reason, the patient will be removed from study and treated at the physician's discretion. The patient will be considered a screen/baseline failure and be replaced. Further data will not be collected if the patient has not begun study treatment at the time of removal from trial. The reason for removal from study will be clearly indicated in EDC Easy®.

If a patient begins treatment and is then removed from treatment for any reason, the patient must be followed per section 7.11.

6.3. Re-screening Patients

A patient who was once classified as a screening/baseline failure for any reason can later be reconsidered for participation, if deemed clinically beneficial for the patient by the treating physician and Principal Investigator. In such case, the patient must again go through the consent process and must be rescreened. The patient must meet each criterion listed on the eligibility checklist based on the clinical documentation in the patient's medical record. After

the patient has reaffirmed his/her desire to participate, the rescreening process must take place within 14 days of Cycle 1, Day 1 (C1D1) as mandated by the treatment start guidelines. Patients who were previously treated with the study drug but were removed from treatment for any reason cannot be reconsidered for participation at a later date. Patients must be re-registered/re-enrolled on the study within 30 days of re-signing the informed consent document.

7. Treatment Plan

7.1. Study Drug Administration

After Cycle #1 a new treatment cycle will be initiated when all of the following conditions are met:

- Non-hematologic treatment related toxicities have improved to grade 1 or resolved (CTCAE v.4.0)
- Platelets $> 10 \times 10^9/L$

Refer to section 7.3 for guidelines for dose modifications based on treatment-related delays and toxicities of the previous cycle.

7.1.1. 765IGF-Methotrexate Administration

765IGF-MTX will be given at the assigned dose as a 1.5 hour IV infusion in 250 ml of 5% dextrose on days 1, 8, and 15 of a four-week treatment cycle. Every 4 week period will be considered one treatment cycle. Subsequent cycles must meet the criteria found in section 7.3.1 and may begin 1 day earlier to accommodate scheduling issues, or up to 4 weeks later if a patient needs this time to recover to meet criteria for start of a new cycle as specified in section 7.2.1. At the investigator's discretion, the study drug may be administered in 10% dextrose rather than 5% dextrose if it is believed necessary to prevent or control hypoglycemia.

Pre-medication

None is required, but can be utilized per clinician discretion. The program of predication below has been used in the prior solid tumor phase I with some of the later enrolled patients to prevent nausea and an allergic reaction. Nausea during infusion was seen in a few patients and a possible allergic reaction to the drug was seen in one patient.

Zofran 8mg PO
Benadryl 50mg PO
Tylenol 650mg PO
Hydrocortisone 100mg IV push
D5 .45 normal saline 100cc/hr to start with premeds

Monitoring

Vital signs including blood pressure, pulse, temperature, respirations, and pulse oximetry, and blood glucose will be measured immediately before the infusion and immediately after completion of the infusion in all patients during all cycles. IGF-MTX causes hypoglycemia at higher dose levels, so it is important to monitor blood glucose levels. During the first 28-day cycle, patients will be monitored for blood glucose on infusion days for a total of 3.5 hours. Vital signs listed above will be monitored per the following table:

Monitoring interval	
Immediately before infusion	All vitals
To Hour 1.5 (during infusion)	Glucose only, every 15 min
Hour 1.5	All vitals
Hours 1.5-3.5	Glucose only, every 30 min

The patients will be provided with a home blood glucose monitoring device and instructed to measure and record blood glucose at 7 hours (\pm 2 hours) and 24 hours (\pm 6 hours) after the start of the infusion. The same device will be used to monitor blood glucose at the clinic during the 3.5 hour monitoring.

On all subsequent cycles that patients are on treatment (i.e., cycle 2 and beyond), those patients that did not experience a severe adverse event during the infusion and 3.5-hr post-infusion period in cycle 1 will be monitored for a total of 2.5 hours on infusion days (i.e., during the 1.5 hour infusion and one hour after termination of the infusion). Vital signs listed above will be monitored per the following table:

Monitoring interval	
Immediately before infusion	All vitals
To Hour 1.5 (during infusion)	Glucose only, every 15 min
Hour 1.5	All vitals
Hours 1.5-2.5	Glucose only, every 30 min

The patients will be instructed to measure and record blood glucose at 7 hours (\pm 2 hours) and 24 hours (\pm 6 hours) after the start of the infusion for each dose.

Patients will be closely monitored for toxicities. Strict I/O will be measured during patient stay both in the ambulatory and inpatient setting (per unit protocol).

Supportive Measures: See also section 7.7

Hypoglycemia will be treated with oral glucose or if necessary IV glucose to maintain blood glucose levels above 50 mg/dl. Acetaminophen for fevers, meperidine for chills, anti-emetics for nausea and vomiting, normal saline or furosemide to maintain fluid balance/blood pressure/pulmonary function, electrolyte replacement, albumin to maintain serum albumin at 3 g/dL or greater. Anaphylactoid reactions will be treated with 100 mg methylprednisolone IV, diphenhydramine 25 mg IV, or 0.3 cc epinephrine (1:1000) IV and transfer to an ICU setting for monitoring. Refer to section 7.2.1. regarding management of Allergic Reaction/Hypersensitivity reactions.

Precautions

Patients should not drive, operate dangerous tools or machinery, or engage in any other potentially hazardous activity that requires full alertness and coordination if they experience sedation while enrolled in this study.

Methotrexate has been reported to cause fetal death and/or congenital anomalies. If a woman becomes pregnant or suspects that she is pregnant while participating in this study, she must inform the investigator immediately and must permanently discontinue study drug. Effective barrier contraception must be practiced during the entire study treatment period and through three months after the last dose of study drug by females

of childbearing potential and male patients (even if surgically sterilized (i.e., status post vasectomy) or the patient must completely abstain from heterosexual intercourse. Refer to section 11.5 for reporting pregnancy in a female patient or the partner of a male patient.

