day	Cycle 1			Cycle 2			Cycle 3 and beyond ²					
	1	8	15		1	8	15		1	8	15	
765IGF-MTX*	X	X	X		X	X	X		X	X ¹	X ¹	
Clinic visit	X	X	X		X	X	X		X	X ¹	X ¹	

* at assigned dose level (see table below)

¹Day 8 and day 15 visits at physician's discretion cycle 3 and beyond

²Treatment continues until disease progression, unacceptable toxicity, patient refusal or other reason as found in section 7.11

Phase I Dose Levels

Dose Level	765IGF-MTX Dose	Number of Patients*
1	0.20 µequivalents per kg	1-9
2	0.40 µequivalents per kg	1-9
3	0.80 µequivalents per kg	1-9
4	1.6 µequivalents per kg	1-9
5	2.5 µequivalents per kg	1-9

*dose escalation cohorts between 1-9 patients; total of 9 patients in MTD cohort. At the discretion of the principal investigator, intra-patient dose escalation between cycles is also allowed but only after 2 cycles at the assigned dose level and confirmation of safety in at least 3 patients treated at the higher dose level.

Abbreviations

Abbreviation	Definition
AE	adverse event
ALT	alanine aminotransferase
AML	acute myelogenous leukemia
ANC	absolute neutrophil count
AST	aspartate aminotransferase
BM	bone marrow
CIR	Cumulative Incidence of Relapse rate
cm	centimeter
CR	complete remission
CRI	Compete remission with incomplete hematologic recovery (same as "marrow CR")
CMMI	Chronic myelomonocytic leukemia
CTCAE	(NCI) Common Terminology Criteria for Adverse Events
CTEP	Cancer Therapy Evaluation Program
dL	deciliter
DFS	time to relapse
DLT	dose-limiting toxicity
ECOG	Eastern Cooperative Oncology Group
EGFR	epidermal growth factor receptor
EFS	Event-Free Response
FDA	Food and Drug Administration
h	hour
HL	Hodgkin Lymphoma
IC50	50% Inhibitory Concentration, the concentration needed to inhibit cell growth by 50%
IGF-1	insulin-like growth factor-1
IGF-1R	insulin-like growth factor-1 receptor
IHC	immunohistochemistry
IND	Investigational New Drug
IRB	institutional review board
kg	kilogram
lb	pound
mg	milligram
min	minute
mL	milliliter
mm ³	cubic millimeters
MDS	myelodysplastic syndrome
MTD	maximum tolerated dose
MTX	methotrexate
NCI	National Cancer Institute
O-AML	Oligoblastic acute myelogenous leukemia
ORR	Overall response rate (= CR rate + CRI rate + PR rate)
OS	Overall Survival rate
PK	Pharmacokinetics studies
PD	Pharmacodynamics studies
PFS	Progression free survival (Time to disease progression or death from MDS, O-AML, or CMML)

PO	per os (by mouth)
PR	Partial Remission
RFS	Relapse-Free Survival
SAE	serious adverse event
US	United States

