3.3.4 Plasma 765IGF Level and 765IGF-MTX toxicity/response

3.3.5 Plasma and whole blood IGF-1R level and 765IGF-MTX Toxicity/Response

3.3.6 Assess formation of antibodies against 765IGF-MTX

3.3.7 Assess formation of neutralizing antibodies

3.3.8 IGF-1R expression level in diseased tissue in bone marrow, as measured by IHC, and flow cytometry, and in blood cells as measured by flow cytometry.

4. Overall Design and Study Plan

This pilot study will evaluate the safety and clinical benefit of 765IGF-MTX in patients with advanced, previously treated MDS, CMML or O-AML. 765IGF-MTX is administered as an IV infusion over 1.5 hours on days 1, 8 and 15 of a 28 day cycle. Treatment continues until disease progression, unacceptable toxicity, or patient refusal. Assessment of response will be confirmed with bone marrow studies performed at the end of cycle 2, and every 8 weeks +/- 7 days (2 cycles) thereafter up to the end of cycle 6, and at physician's discretion thereafter.

- Dose Finding Component: Up to 5 dose levels will be tested (refer to schema on page 6). The maximum tolerated dose (MTD) will be determined using the modified toxicity probability interval design with dose limiting toxicity (DLT) estimated at 0.33.

Our modification involves using cohorts of size 1 for the initial doses, which allows rapid escalation through the initial dose levels, and expanding to cohorts of size 3 once any grade 2 or higher toxicity is observed that is considered related to study drug (with the exception of alopecia, nausea, or diarrhea). Additional patient cohorts will not be enrolled until 1 of 1 (with no grade 2 toxicity), 3 of 3, 5 of 6, or 7 of 9 patients at the current dose level complete all planned treatment for cycle 1 (defined as 3 doses of 765IGF-MTX without DLT and are able to start cycle 2 with no more than a 2 week delay. At the discretion of the principal investigator, intra-patient dose escalation between cycles is also allowed but only after 2 cycles at one dose level and confirmation of safety in at least 3 patients treated at the higher dose level.

If none of the dose levels are acceptable at study completion, an optimal dose level will not be identified and the drug does not warrant further investigation.

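### The shorter 2.5 h infusion-day observation, granted on cycle 1 tolerance, is not reset when a patient's dose is raised (minor, patient safety)

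*Combined protocol and SAP*

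**What the plan says.** Section 7.1.1 sets the cycle 1 rule: "patients will be monitored for blood glucose on infusion days for a total of 3.5 hours". The infusion takes 1.5 h, and glucose is then read every 30 minutes from hour 1.5 to hour 3.5.

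For later cycles the rule opens with the condition "On all subsequent cycles that patients are on treatment (i.e., cycle 2 and beyond), those patients that did not experience a severe adverse event". The window in which such an event counts is given as "during the infusion and 3.5-hr post-infusion period in cycle 1". Patients who meet the condition "will be monitored for a total of 2.5 hours on infusion days". The matching table reads glucose every 30 minutes from hour 1.5 to hour 2.5. The section gives no later-cycle table for patients who did have such an event.

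The footnote to the Phase I dose-level table in the synopsis permits dose increases within a patient at the principal investigator's discretion, "only after 2 cycles at the assigned dose level and confirmation of safety in at least 3 patients treated at the higher dose level". Section 4 repeats this.

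Section 7.7 places the infusion and the following 1 to 2 h in a monitored room with intravenous diazepam at hand. It refers back to 7.1.1 for the duration, so the time in that room follows whichever table applies.

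**The concern.** The shorter schedule rests on what the patient tolerated in cycle 1, at the dose then given. If the dose is later raised, that evidence comes from a lower dose, yet the shorter schedule stays in force.

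The protocol itself links the main acute risk to dose: "IGF-MTX causes hypoglycemia at higher dose levels, so it is important to monitor blood glucose levels". The dog study in section 1.2.1 points the same way. It found no significant treatment-related toxicity at 0.2 and 0.5 µeq/kg, but hypoglycemia and anaphylactoid reactions at 2 and 6 µeq/kg. Section 10.1.8 adds that syncope and seizure, among other events, have occurred during infusion or up to 3 h after it.

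What is at stake is one hour of observation at a first exposure to a higher dose. Every patient who enters at that level has that hour in cycle 1. A patient who reaches the level by escalation is not required to have it.

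**Working it through.** **Inputs.** Infusion 1.5 h; total observation 3.5 h (cycle 1) and 2.5 h (later cycles); glucose every 15 min during infusion and every 30 min after it; home readings at 7 h (± 2 h) and 24 h (± 6 h) from the start of infusion (all section 7.1.1). Dose levels 0.20, 0.40, 0.80, 1.6 and 2.5 µeq/kg (synopsis).

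**1. Observation after the infusion** (total minus infusion time). This agrees with the plan's own tables.
- Cycle 1: 3.5 − 1.5 = 2.0 h
- Later cycles: 2.5 − 1.5 = 1.0 h

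**2. Glucose readings after the infusion**
- Cycle 1: hours 2.0, 2.5, 3.0 and 3.5, so 4
- Later cycles: hours 2.0 and 2.5, so 2

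Counting the end-of-infusion reading at hour 1.5 makes this 5 against 3; the difference is still 2.

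**3. Clinic glucose readings per infusion day** (before + during + at end + after)
- Cycle 1: 1 + 5 + 1 + 4 = 11
- Later cycles: 1 + 5 + 1 + 2 = 9

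**4. Gap from the last clinic reading to the first home reading** (home reading at 5 to 9 h)
- Cycle 1: 5 − 3.5 = 1.5 h to 9 − 3.5 = 5.5 h
- Later cycles: 5 − 2.5 = 2.5 h to 9 − 2.5 = 6.5 h

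**5. When a first higher dose can occur.** Escalation is between cycles and needs 2 completed cycles, so the earliest is cycle 3 day 1. The later-cycle table already governs that day. Sections 4, 7.1.1, 7.2 and 7.7 contain no rule that switches the table back.

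**6. Size of a one-level step.** 0.40/0.20 = 0.80/0.40 = 1.6/0.80 = 2.0-fold; 2.5/1.6 = 1.56-fold.

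**7. Experience that offsets the risk**
- In the patient: 2 cycles × 3 doses = up to 6 infusions at the lower dose.
- At the higher level: the plan does not define confirmation of safety for this purpose. If the cohort standard in section 4 is borrowed ("3 of 3, 5 of 6, or 7 of 9 patients at the current dose level" completing cycle 1 treatment), the minimum is 3 patients × 3 doses = 9 infusions, all observed under the 3.5 h table.

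**8. What the second hour adds.** The cycle 1 table lists glucose only between hours 1.5 and 3.5. The gain is therefore 2 glucose readings and continued presence in the monitored room, with no further scheduled vital signs.

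**The case against.** The strongest reply is that the longer table was never tied to a dose level. Section 7.1.1 ties it to the first 28-day cycle, that is, to first exposure to the drug. An escalated patient is not drug-naive, and the protocol nowhere promises equal observation at each level. This stands: the comparison with a patient starting at the higher level shows a difference in protection, not a breach of a stated principle.

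The second reply is that the named hazard is already covered. Section 10.1.8 expects low blood sugar straight after the drug, and both tables read glucose through the infusion, at its end and for the next hour. Home readings follow each dose. The vehicle is dextrose, and the drug may be "administered in 10% dextrose rather than 5% dextrose if it is believed necessary to prevent or control hypoglycemia". Escalation also waits for confirmed safety in at least 3 patients. Most of this stands, and it keeps the point minor. But the dextrose, the 15-minute checks and the home readings also apply in cycle 1, where the plan still requires the second hour. Three patients are also limited reassurance: with no events in 3, the one-sided 95% upper bound on the event rate is 1 − 0.05^(1/3) = 63%.

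A third reply is that investigators may observe for longer and are told in general terms to monitor closely. That permits the extra hour without requiring it.

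A reader might also infer that a severe event outside the cycle 1 window leaves a vulnerable patient on the short schedule and open to escalation. The documents give this little support. Section 7.2.1 calls for a lower dose or discontinuation after clinically significant grade 3 or higher treatment-related non-hematologic toxicity, with limited gastrointestinal exceptions. It also ends treatment after a grade 3 or 4 allergic reaction. Such patients are unlikely candidates for a higher dose.

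**Conclusion.** The gap is real and minor. Followed exactly, section 7.1.1 gives an escalated patient 1 h less observation and 2 fewer glucose readings after each infusion at the new dose than a patient who starts there.

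Two stronger conclusions are not supported:
- A reader might infer that toxicity assessment for dose finding is weakened. It is not: section 4 counts DLTs in cycle 1, when the 3.5 h table applies.
- A reader might infer that events are known to be missed in the second hour. Section 10.1.8 gives only an outer limit of 3 h, and the available text does not place any event in that hour. The third hour is outside both tables.

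The conclusion assumes that the 3.5 h window in the later-cycle rule runs from the start of infusion, as in the cycle 1 table; the rule's wording could be read as 3.5 h after the infusion. The alternative would change which events disqualify a patient, not the counts above. The number of escalated patients is not stated and may be zero.

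**What to change.** Add to section 7.1.1:

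*During the first cycle after any intra-patient dose increase, the cycle 1 monitoring table (3.5 h) applies. If no severe adverse event occurs during the infusion and post-infusion observation in that cycle, the 2.5 h table applies in later cycles at that dose or a lower one.*

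The last words settle what happens if the dose is later reduced. Through the cross-reference in section 7.7, the stay in the monitored room lengthens as well, with no separate edit.

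The cost is two sentences and no new procedure. Each infusion in the cycle after an increase takes 1 more hour and 2 more glucose readings: up to 3 × 1 = 3 h and 3 × 2 = 6 readings per dose increase if that cycle is free of severe events. It may be less, because day 8 and day 15 visits are at the physician's discretion from cycle 3. It is more only if a severe event occurs and treatment continues, when longer observation is appropriate anyway.

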7.11. Follow-up

Administration of study medication will be continued after cycle 2 until disease progression, unacceptable toxicity, or patient withdrawal. A final study visit will occur 30 days (+/-1 week) after the last dose of 765IGF-MTX. This visit will end study participation unless there is ongoing toxicity at least possibly related to study treatment. In this case, the patient will be followed as medically appropriate until resolution or stabilization of the adverse event.

8. Study Parameters

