8.1. Standard of Care Procedures

	Baseline, within 28 days of enrollment	Each treatment cycle ^a			Every 8 weeks (± 1 week)	30 days (± 1 week) after final dose of 765IGF-MTX ¹
		Day 1 ² (±1 day)	Day 8 (±1 day)	Day 15 (±1 day)		
Signed consent (Registration/ Enrollment must occur within 30 days.)	X					
Medical history	X	X				X
Review of prior therapy	X					
Bone marrow biopsy and aspirate confirming disease and blast count ³	X				X ³	
Physical exam	X	X				X
Vital signs	X	X	X	X		X
Height, weight	X	X				X
Concomitant meds review	X	X	X	X		X
Performance status	X	X				X
Symptom and toxicity	X	X	X	X		X ³
CBC w/ diff	X	X	X	X		X
CMP (with: calcium, glucose, sodium, potassium, CO ₂ , chloride, BUN, creatinine, albumin, ALT, AST, bilirubin, alkaline phosphatase, total protein)	X	X	X	X		X
Uric acid (cycle 1 only)	X	X		X		
LDH	X	X				
HbA1C for diabetic patients	X					X
Serum pregnancy test for females of child- bearing potential	X					
ECG ⁴	X	X				X
765IGF-MTX administration			X	X		

^a Subsequent cycles beyond cycle 1 must meet the criteria found in section 7.3 and may begin 1 day earlier or up to 2 days later to accommodate scheduling issues.

¹ For patients who leave treatment with a response, repeat appropriate disease assessment every 6-12 weeks until progression or start of a new treatment.

² For cycle 1 only, tests and procedures do not need to be repeated if done within 3 days of day 1.

³ Bone marrow biopsy should be at end of end of cycle 2, and every 2 cycles thereafter to cycle 6. Patients who achieve response (CR) could have repeat bone marrow biopsies per MD discretion.

⁴ ECG performed at screening, at cycle 1 and at the end of study visit 30 days after the final dose.

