11.5 Procedures for Reporting During Pregnancy and Birth Events

If a woman becomes pregnant or suspects that she is pregnant while participating in this study, she must inform the investigator immediately and must permanently discontinue study drug(s). All pregnancies and suspected pregnancies must be reported to the IGF Oncology Clinical Operations team immediately using a Pregnancy Report Form (see Section 11.3 for contact information). The pregnancy must be followed for the final pregnancy outcome (i.e., delivery, still birth, miscarriage) and the IGF Oncology Operations team will request this information from the investigator.

If a female partner of a male patient becomes pregnant during the male patient's participation in this study, this must be reported to the IGF Oncology Clinical Operations team immediately using a Pregnancy Report Form (see Section 11.3 for contact information). Every effort should be made to follow the pregnancy for the final pregnancy outcome.

12. Study Data Collection and Monitoring

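### Contraception is required to 3 months after the last dose, but the duty to inform and the partner-pregnancy rule stop with study participation, at about 30 days

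*Combined protocol and SAP*

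**What the plan says.** **Risk window.** Inclusion criterion 5.1.9 and the precautions in 7.1.1 both run contraception to 3 months after the last dose. Section 7.1.1 puts it as "Effective barrier contraception must be practiced during the entire study treatment period and through three months after the last dose of study drug", for females of childbearing potential and for male patients, and then refers to 11.5 for pregnancy in a patient or partner.

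**Duty to inform.** Section 11.5 opens with "If a woman becomes pregnant or suspects that she is pregnant while participating in this study"; she must then tell the investigator at once and stop study drug for good. The same duty, with the same limit to participation, stands in 7.1.1 and 10.1.9.

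**Partner rule.** Section 11.5 covers a partner who conceives during the male patient's "participation in this study, this must be reported to the IGF Oncology Clinical Operations team immediately".

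**End of participation.** Section 7.11 sets a final visit 30 days (plus or minus 1 week) after the last dose. It adds: "This visit will end study participation unless there is ongoing toxicity at least possibly related to study treatment".

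**Sentence without a time limit.** Section 11.5 also says "All pregnancies and suspected pregnancies must be reported" to the sponsor's team, and asks for follow-up to the outcome.

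**Testing.** Exclusion criterion 5.2.8 asks for a negative serum "pregnancy test result obtained during screening". In the 8.1 schedule, the row "Serum pregnancy test for females of child- bearing potential" carries one mark. The conditions for starting a new cycle, in 7.1 and 7.2.1, are recovery from non-hematologic toxicity and a platelet threshold.

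**The concern.** The protocol fixes its own period of reproductive risk at treatment plus 3 months, and 5.2.8 places methotrexate in Pregnancy Category X. The provisions by which a pregnancy would come to light should cover the same period. They end about two months sooner, because they are tied to participation and participation ends at the 30-day visit.

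After that visit a male patient must still use contraception, but no explicit rule covers a pregnancy in his partner. A woman must still use contraception, but her stated duty to tell the investigator has lapsed. A pregnancy in that period could go unreported and its outcome unfollowed.

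During treatment there is a related, smaller weakness. Stopping the drug depends on the woman knowing or suspecting that she is pregnant, and the visible text shows no test after screening that would tell her.

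**Working it through.** The plan gives no figure on this point. The check compares the sections and does some calendar arithmetic.

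**1. Post-treatment window**

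Inputs: contraception to 3 months after the last dose (5.1.9, 7.1.1), taken as 90 days; final visit at day 30 plus or minus 7 after the last dose (7.11), so day 23 to day 37.

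Uncovered days = 90 minus day of final visit.

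| Final visit | Uncovered days | Share of 90 |
|---|---|---|
| Day 23 | 90 − 23 = 67 | 74% |
| Day 30 | 90 − 30 = 60 | 67% |
| Day 37 | 90 − 37 = 53 | 59% |

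This applies to patients whose participation ends at the final visit. Those with ongoing, possibly related toxicity stay in participation for longer.

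**2. What still operates in those days**

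- The reporting sentence in 11.5 without a time limit: yes, for a pregnancy the site has learned of.
- The woman's duty to inform: no, since all three statements of it are limited to participation.
- The partner rule: no, for the same reason.
- A scheduled pregnancy enquiry: none in the visible text.
- Responders' visits: footnote 1 of 8.1 reads "For patients who leave treatment with a response, repeat appropriate disease assessment every 6-12 weeks until progression or start of a new treatment". Counted from the last dose, that is day 42 to day 84, inside the window. It is disease assessment, with no pregnancy question listed, and it does not cover non-responders.

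**3. Age of the only visible test during treatment**

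Assumptions: test 0 to 28 days before cycle 1 day 1, taking enrollment and that day as the same; 28-day cycles with no delay.

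- Cycle 2, day 15 dose is study day 28 + 15 = 43, which is 42 days after day 1. Test age is 42 + 0 = 42 to 42 + 28 = 70 days, at the sixth dose (2 × 3).
- One 4-week delay before cycle 2, the longest that 7.2.1 allows, raises the upper figure to 70 + 28 = 98 days.
- Cycle 6, with only day 1 given from cycle 3: the last dose is 5 × 28 = 140 days after day 1. Test age is 140 to 168 days, after 6 + 4 × 1 = 10 doses.
- Cycle 6, with every dose given: the last dose is 140 + 14 = 154 days after day 1. Test age is 154 to 182 days, after 6 + 4 × 3 = 18 doses.

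**4. The same measure with a day 1 test in each cycle**

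- Day 1 to day 15 is 14 days. With the visit windows of plus or minus 1 day in 8.1, it is at most 14 + 1 + 1 = 16.
- In cycle 1, if the 3-day allowance in footnote 2 of 8.1 is used, 14 + 3 = 17 days, or 18 if day 15 falls a day late.

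**The case against.** The strongest reply is that 11.5 already requires every pregnancy to be reported, with no end date and with follow-up to outcome. Section 7.1.1 points to 11.5 right after stating the 3-month rule, so a site may well read the two together. This stands in part. A reader might infer that a pregnancy after the final visit need not be reported at all, and the documents do not support that. What the sentence does not supply is a way for the site to learn of the pregnancy, or an explicit rule for partners after participation.

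Other safeguards exist. Section 10.1.9 advises against use in women of childbearing potential unless benefit clearly outweighs risk. Section 11.4 makes related SAEs reportable at any time. History and examination are scheduled on day 1, and symptoms and medication are reviewed on days 1, 8 and 15 (days 8 and 15 being discretionary from cycle 3). These help. But a pregnancy is not itself a listed serious outcome in 11.1, the late-SAE rule needs an event and a judgement that it is related, and none of these is a test or a post-treatment enquiry.

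A reader might also infer that contact with non-responders stops at day 30. That goes too far: 13.2.1 estimates mortality at landmarks such as 90 and 180 days, so survival status is expected later. The visible text does not schedule that contact or attach a pregnancy question to it.

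On testing, the 8.1 table as extracted has lost marks (the drug row has none on day 1), so its single pregnancy mark is weak evidence alone. Section 5.2.8 and the new-cycle conditions agree with it, though an eligibility rule and toxicity-recovery rules need not list on-treatment tests. The consent pages and some text beside the sponsor row of the 11.3 reporting table could not be read and may hold further instructions.

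**Conclusion.** The mismatch holds on the visible text. For a patient whose participation ends at the final visit, about 60 of 90 days (53 to 67) of the required contraception period have no explicit duty to inform, no partner rule and no scheduled enquiry. The figure rests on taking 3 months as 90 days and on nothing in the unread pages filling the gap.

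The testing point is a reasonable addition of lower certainty. The test ages are calendar time and not a measure of risk. The documents do not say how many females of childbearing potential, or men with partners who could conceive, will be treated, and the number may be small.

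A reader might infer that 5.1.9, which lists hormonal methods as examples, contradicts the barrier rule in 7.1.1. It does not: following 7.1.1 satisfies both. Nor does anything here bear on the DLT rules, the sample size or the efficacy analysis. This is a minor, inexpensive patient-safety improvement.

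**What to change.** 1. In 7.1.1, 10.1.9 and 11.5, keep the present start of the duty to inform and of the partner rule, and extend only the end, so that both run during participation and through 3 months after the last dose. All three sections need the edit, or the protocol will contradict itself. The start should not move to the first dose: section 6 places enrollment before any treatment, so the present wording already covers that interval.
2. In 7.11, add one telephone enquiry at 3 months after the last dose for male patients and females of childbearing potential.
3. In 8.1, add a serum pregnancy test for females of childbearing potential on day 1 of each cycle (the 3-day allowance in footnote 2 can serve for cycle 1) and at the 30-day visit. In 7.1 and 7.2.1, add a negative result to the conditions for a new cycle.

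The cost is text changes in 7.1, 7.1.1, 7.2.1, 7.11, 8.1, 10.1.9 and 11.5, one assay per cycle and one at the 30-day visit, and one call per patient concerned. Blood is already drawn for CBC and chemistry at those visits. The total cannot be stated, because the documents do not give the number of such patients.
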